1.4. How frequently do these hernias occur?

A systematic review for this trial exploring hernias at the closure of stoma sites revealed that hernias occur in up to 30% of patients undergoing stoma reversal and that when present, nearly half require subsequent surgical repair. Most of the studies identified as part of this systematic review considered stoma site hernias as a secondary endpoint. The studies that considered it as a primary endpoint showed a higher rate (hernia rate of 30%)²⁻⁴ than the secondary endpoint papers (hernia rate 8%)¹¹. Furthermore, when clinical findings and results from CT scans were combined, an even higher incidence was found. It is recognised that over time, incisional hernias can increase in size and become increasingly symptomatic⁹. The data suggests that CT scans may precede the onset of symptoms from the hernias – that is, the CT scan may detect the hernia earlier than the patient will

report it. An exploratory analysis comparing radiological hernia rate with clinical hernia rate will assess this possibility in the ROCSS trial.

There is limited research concerning the post-operative symptoms following stoma site closure, although they may be expected to have a similar profile to incisional and parastomal hernias^{9 10}. Such complications include pain and intestinal obstruction, which may necessitate emergency surgery.

The concept of prophylactic prevention of parastomal hernias has been assessed in a small randomised trial, which reported a greater than 50% reduction in herniation¹². However, prophylaxis of hernias when reversing stomas has not been assessed and a randomised trial is therefore warranted.

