4.2. Secondary Objectives

The secondary objectives of the ROCSS trial are to:

- Assess radiological hernia rates at one year post randomisation.
- Assess surgical re-intervention rates.
- Assess the frequency of wound infections and seroma associated with the mesh.
- Assess the impact of the mesh on a patient's quality of life and any pain experienced. Quality
 of life is an important secondary outcome measure, as the re-operation rate may be low, as
 even if a clinical hernia is diagnosed, the decision for surgical re-intervention has to take into
 account the patient's age, any co-morbidities and patient preference.
- Determine the cost effectiveness of the mesh insertion in stoma site closure and management of subsequent hernias.
- Conduct an exploratory analysis to investigate the CT scan as an early surrogate marker of late clinical herniation. Radiological hernia rate at one year post randomisation will be compared with the clinical hernia rate at two years to assess the value of using a CT scan as an early diagnostic tool of herniation. This will identify to other investigators that this is a potential area of clinical need and allow earlier reporting of future studies.

5. Outcome Measures

The outcome measures of the phase III trial will be:

Primary outcome

1. Rate of clinically detectable hernias at two years post-randomisation.

Secondary outcome measures

- 1. Radiological hernia rate at one year post-randomisation. An exploratory analysis will also compare radiological hernia rate at 1 year with clinical hernia rate at 2 years to assess the value of using a CT scan as an early diagnostic tool of incisional hernias.
- Incidence of developing a symptomatic hernia evaluated at 12 and 24 months postrandomisation. The clinical detection of hernias defined by palpable fascial defects, and global weaknesses around closed stoma sites without palpable fascial defects, will be recorded. Patient-reported hernia symptoms including a local lump or pain at the site of the stoma closure will also be collected.
- 3. Surgical re-intervention rates at 2 years post-randomisation.
- 4. Surgical complications, including wound infections at 30 days post-operatively and at 1 year post-randomisation, and seroma formation at 1 year post-randomisation.
- 5. Quality of life assessed using EuroQol EQ-5D at baseline, 30 days post-operatively, 12 and 24 months post-randomisation.

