10.1. Clinical Follow-Up Visits

Patients will be seen at 30 days post-op (+/- 5 days) to assess wound healing and surgical complications. Patients will then be reviewed at 12 months post-randomisation (+/- 3 months) for radiological and clinical assessment, with a final clinical assessment at 24 months post-randomisation (+/- 1 month). Any other follow-up will be at the discretion of the clinical team.

Follow-up clinical assessments will be performed by a surgeon, qualified to MRCS level or above. This should be standard practice however in cases where a MRCS level is not possible, a surgeon with MRCS equivalent or a nurse who has completed a physical examination course as part of a masters degree or similar may undertake the clinical examination.

MRCS equivalence and nurse qualification is assessed by the local PI and demonstrated by the delegation of the clinical examination duty.

Clinical examination assessors are to be blinded to the randomised allocation."

Below is the recommended standardised clinical examination technique for the closed stoma site.

Clinical examination

- 1. The patient should be examined according to this scheme in both standing and lying positions.
- 2. The patient should perform either a Valsalva manoeuvre or a forceful cough, whilst the placing of a hand over the closed stoma site.
- 3. You should record if the patient has:
 - a. A palpable fascial defect with or without protrusion of bowel or fat;
 - b. A global weakness around the stoma scar, without palpable fascial defect.
- 4. If in doubt, a second blinded clinician should be consulted and consensus achieved.

Definition of a hernia

For this study, a clinical hernia is defined as a palpable or visible discrete protrusion at the site of the stoma closure, possibly with a palpable fascial defect. A clinically global weakness is defined as a palpable or visible generalised weakness/ protrusion, which takes on no discrete nature and where no

fascial defect is palpable. A radiological hernia is defined as any breach in the abdominal wall muscles or fascia visible on CT scan, with or without the passage of bowel, omentum or fat through it.

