13.3. Exploratory Data Analysis

ROCSS

An exploratory analysis will compare the radiological hernia rate at 1 year with clinical hernia rate at 2 years. This will provide useful information on the value of using a CT scan as an early diagnostic tool of herniation, which could then be used in future abdominal wall studies as a surrogate endpoint for clinical hernia. Correlation between CT and clinical hernia rates will be calculated as follows:

- The proportion of false negatives i.e. clinical but not radiological hernias
- The proportion of false positive i.e. radiological but not clinical hernias (at 2 years)

An additional analysis will correlate patient reported symptoms at the closed stoma site to clinical examination and CT findings.

14.Data Monitoring

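### Section 13.3 assesses the 1-year CT only by two discordance proportions against 2-year clinical hernia; these neither isolate diagnostic accuracy nor test surrogacy (low severity, exploratory)

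*Protocol*

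**What the plan says.** Section 4.2 of the protocol lists a secondary objective to "investigate the CT scan as an early surrogate marker of late clinical herniation". Section 13.3 repeats the surrogate aim for future abdominal wall studies and adds a diagnostic one: "This will provide useful information on the value of using a CT scan as an early diagnostic tool of herniation".

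The comparison is fixed in section 13.3: "An exploratory analysis will compare the radiological hernia rate at 1 year with clinical hernia rate at 2 years". The correlation between the two is then to be calculated as two proportions:

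- "The proportion of false negatives i.e. clinical but not radiological hernias"
- "The proportion of false positive i.e. radiological but not clinical hernias (at 2 years"

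Only the second line carries a time point, and neither states a denominator. Section 13.3 does not say whether the proportions are given by arm or how a repaired hernia is classified.

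Section 10.1 schedules a clinical assessment alongside the CT, with patients "reviewed at 12 months post-randomisation (+/- 3 months) for radiological and clinical assessment". Section 13.3 does not use that 12-month examination in the two proportions. Section 10.1 also defines the two kinds of hernia differently: on CT any breach of muscle or fascia counts, whereas a clinical hernia needs a discrete protrusion that can be felt or seen.

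**The concern.** The terms false positive and false negative describe test error when test and reference look at the same disease state. Here the state can change between them. The protocol says that stoma site hernias occur over time (section 1.1), that incisional hernias can enlarge, and that CT may show them before the patient reports them (section 1.4). A hernia that forms after the scan, and a breach on CT that is not yet palpable at 24 months, both fall in the error cells even if the scan was read perfectly. As a statement about a diagnostic tool, the two proportions cannot separate scan error from disease course.

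For the surrogate aim the difficulty is different. Two discordance proportions are not a correlation, and they do not show whether a trial reporting the CT endpoint would estimate the same treatment effect as one reporting the clinical endpoint. Section 4.2 wants this analysis to allow earlier reporting of future studies, so that is the question that matters.

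**Working it through.** The protocol states no figure for this analysis, so there is none to reproduce. The checks below use its windows and published results.

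**1. Time between assessments (section 10.1).** The CT falls at 12 ± 3 months, that is 9 to 15. The final examination falls at 24 ± 1 months, that is 23 to 25.

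- Shortest gap: 23 − 15 = 8 months
- Longest gap: 25 − 9 = 16 months
- CT to the 12-month examination, which shares the CT window: at most 15 − 9 = 6 months, and nominally the same review

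**2. Mesh effect on each endpoint (Protocol Summary, Findings).**

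| Endpoint | Mesh | Control | Difference | Crude RR |
|---|---|---|---|---|
| CT, 1 year | 20/229 = 8.7% | 47/226 = 20.8% | 12.1 points | 0.42 |
| Clinical, 2 years | 39/323 = 12.1% | 64/327 = 19.6% | 7.5 points | 0.62 |

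With the arms combined, CT gives 67/455 = 14.7% and examination 103/650 = 15.8%, which looks like close agreement. By arm, CT is 3.4 points below the clinical rate with mesh (8.7 − 12.1) and 1.2 points above it in control (20.8 − 19.6). A combined table could therefore look reassuring whatever the arms show. The denominators differ (455 and 650) and the adjusted intervals overlap (0.26–0.69 and 0.43–0.90), so this illustrates the point and does not establish a discrepancy.

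**3. How far disease course alone could fill the error cells.** This is hypothetical, because the cross-classified counts are not in the protocol. Assume that the clinical rate of 15.8% applies to the 455 scanned patients (about 72 hernias), that there are 67 CT hernias, and that CT misses nothing present at the scan. Let f be the share of the 72 that arise after the scan.

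- False-negative share of clinical hernias = f
- False-positive share of CT hernias = [67 − 72(1 − f)] / 67

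| f | False-negative share | False-positive share |
|---|---|---|
| 10% | 10% | 3% |
| 20% | 20% | 14% |
| 30% | 30% | 25% |
| 40% | 40% | 36% |
| 50% | 50% | 46% |

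For example, at f = 30%, 72 × 0.7 = 50.4 and (67 − 50.4)/67 = 25%. A scan with no detection error could thus show sizeable values in both cells. The value of f is unknown.

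**4. Repair.** Section 9.1 records re-operations with their indications, but no rule places a repaired hernia in the table. The outcome is worded as a rate at two years in section 5, and as hernia within 24 months in the Interpretation of the Protocol Summary, so either a prevalent or a cumulative reading is open. If a repaired hernia counted as not clinical, assumed repair shares of 5, 10, 20 and 30% of the 67 CT hernias would move about 3, 7, 13 and 20 patients into the false-positive cell.

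**The case against.** The strongest reply is that the gap is deliberate. The objective in section 4.2 concerns late clinical herniation. For that target, a hernia that appears after a negative scan is a genuine miss by the surrogate, and a CT hernia that is not clinical at 2 years is a genuine false alarm for that endpoint. This stands. A reader might infer that section 13.3 gives the surrogate objective a wrong answer by counting such patients as errors. The protocol does not support that, and relabelling them as something other than misses would flatter CT.

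Three further inferences also go beyond the text:

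- **Repairs and pooling.** Section 13.3 does not say that repaired hernias are false positives or that the arms are pooled. It is silent on both, and a statistical analysis plan that was not available for this review may settle them.
- **Number of repairs.** Section 1.4 reports of such hernias that "when present, nearly half require subsequent surgical repair". Applying this to the 67 CT hernias would be unsafe. The figure comes from a literature review, has no time limit, and says nothing about repair between the scan and month 24. In this trial, surgical reintervention over the whole two years was (42 + 54)/(344 + 346) = 96/690 = 13.9%.
- **Treatment effects.** The two relative risks do not show that CT and examination differ in the mesh effect, for the reasons given in the working.

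It is also fair to say that section 13.2 already plans the CT comparison by arm and that the protocol reports both effects. Section 13.3 nevertheless does not bring them together for the surrogate question. Finally, comparing CT with the 12-month examination does not remove the difference in definitions: a breach seen on CT but not palpable would still be discordant. It does remove most of the time gap, and the remaining difference can be stated.

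**Conclusion.** The point holds in a limited form. Section 13.3 prescribes two discordance proportions between assessments 8 to 16 months apart that use different definitions. As diagnostic accuracy, they mix scan error with disease course. As a test of surrogacy, they are incomplete, because they do not compare the treatment effects on the two endpoints.

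The size of the mixing cannot be derived from the protocol; the ranges in the working rest on assumed shares. The repair element arises only if the 2-year outcome is read as prevalent at the visit. Severity is low: the analysis is labelled exploratory, the trial has reported, and the published primary result does not depend on it. The change is still worth making, because it is cheap and makes a named secondary objective answerable.

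**What to change.** Amend section 13.3 as follows.

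1. **Accuracy.** Report the CT against the blinded clinical examination at the same 12-month visit. Keep the terms false positive and false negative for this comparison, and state that the two definitions differ.
2. **Prediction.** Report the 1-year CT as a predictor of clinical hernia up to 24 months, with sensitivity, predictive values and stated denominators. Count a closure-site hernia found at 12 months, or repaired before 24 months, as a clinical hernia. Keep hernias that appear after a negative scan as misses by the surrogate, and show separately those absent at the 12-month examination.
3. **Surrogacy.** Report both by arm, and set the mesh effect on CT beside the mesh effect on clinical hernia in the patients who have both assessments.

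The 5–8 year extension should not serve as the reference for this. Its hernia information comes from telephone report and medical records, without a trial physical examination (sections 19.4 and 19.10), so it is a different endpoint.

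The cost is a little more analysis work. The 12-month examination, the CT reads and the re-operations with indications are already scheduled for collection. Because the main results are known, the additions should be labelled post hoc.

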14.1. Data Monitoring and Ethics Committee

During the study, interim analyses of safety and outcome data will be supplied, in strict confidence, to an independent DMEC along with any other analyses that the committee may request.

The DMEC will meet once the first 90 patients have been entered into the study or at the end of the 12 month feasibility part whichever occurs first to assess the safety data, and advise on continuation to the main phase III trial. Since this is an internal feasibility study, and this safety data will be included in the main analysis of the ROCSS trial, this data will remain confidential, except to members of the DMEC.

During the main phase III trial, the DMEC will meet annually, or more frequently if considered appropriate, and will advise the chair of the Trial Steering Committee if, in their view, the randomised comparison in ROCSS has provided both (a) "proof beyond reasonable doubt" that for all, or for some types of patient, treatment with the collagen mesh is clearly indicated or clearly contraindicated in terms of a net difference in the main outcome measures, and (b) evidence that might reasonably be expected to influence the patient management by many clinicians.

The Trial Steering Committee can then decide whether to modify the study protocol. Unless this happens, however, the steering committee, the collaborators and all of the central administrative staff (except the trial statisticians who supply the confidential analyses) will remain ignorant of the interim results.

If the clinical coordinators are unable to resolve any concerns satisfactorily, collaborators, and all others associated with the study, may write through the ROCSS trial office to the chair of the DMEC,

drawing attention to any worries they may have about the possibility of particular side-effects, or of particular categories of patient requiring special study, or about any other matters thought relevant.

15. Health economics analysis

In general terms, the aim of the economic evaluation is to determine the cost-effectiveness of using a collagen tissue matrix compared to standard closure techniques for patients undergoing elective closures of stomas, and to establish the lifetime cost and outcomes associated with either collagen tissue matrix or usual closure of stoma sites.

The health economic analysis has two distinct parts. The first part is a cost-effectiveness analysis conducted alongside the randomised clinical trial. The second part is a model-based cost-effectiveness analysis building on the trial-based analysis and using published data on long-term outcomes and costs. Although the trial-based analysis is important in determining costs, quality of life, and cost-effectiveness over the first two years after the intervention, the model-based analysis will provide the most useful information to decision makers in estimating the long-term impact on costs and patient outcomes.

15.1. Trial-based cost-effectiveness analysis

The base-case economic evaluation to be conducted alongside the randomised clinical trial will estimate the relative cost-effectiveness of using a collagen tissue matrix compared to standard closure techniques for patients undergoing elective closures of stomas (ileostomy or colostomy). The primary within-trial cost-effectiveness analysis will estimate the cost per hernia clinically detected and cost per additional quality adjusted life (QALY) year gained, both over a two-year period, matching the time point for the primary clinical outcome. The base-case cost-utility analysis will estimate the cost per additional quality adjusted life (QALY) year gained using data from the full 12 month follow-up. Cost and outcome data will be collected on every patient within the trial.

15.1.1. Cost data

Data will be collected using a short questionnaire from a representative sample of hospitals to ensure generalizability. Data on resource use associated with each strategy will be collected and will include information on supplies (collagen mesh), length of pre and post-operative hospital stay, drugs, time(days) to return to normal activities, length of hospital stay due to adverse effects, equipment and staff involved in pathways for each strategy. Unit costs for supplies, inpatient stays, drugs, equipment and staff will be collected from published sources such as the National Health Service (NHS) Schedule of Reference Costs, Unit Costs of Health and Social Care (PSSRU), British National Formulary (BNF) and local estimates where possible.

15.1.2. Outcome data

Outcome data from the trial will be the incidence of clinically detectable closure site hernias at 2years. EQ-5D data will be collected from each patient at baseline (pre-operation), at 30 days postoperation and at 12 and 24 months post-randomisation in order that QALYs can be calculated using the UK tariff (Dolan, 1997)

15.1.3. Analysis

A cost-consequences analysis will initially be undertaken. This will detail all costs and outcomes for 30 days post-operative, 12 months and 24 months follow-up. For each trial arm, mean costs and outcomes and their 95% confidence intervals will be presented. An incremental cost-effectiveness analysis will be undertaken from an NHS perspective to determine the cost per hernia clinically detected and cost per additional quality adjusted life (QALY) year gained, both over a two-year period. Incremental cost effectiveness ratios (ICERs) will be estimated by dividing the difference in mean cost between two treatments by the difference in mean outcomes.

Non-parametric bootstrapping will be used to illustrate and quantify uncertainty. 5000 paired estimates of mean differential costs and outcomes will be estimated and presented graphically on a cost-effectiveness plane. To determine the probability of a treatment being deemed cost-effective compared to an alternative treatment, cost-effectiveness acceptability curves (CEAC) will be constructed. This shows the probability that an intervention is cost-effective, relative to the chosen comparator, across a range of values that represent a decision makers' willingness to pay for an additional unit of outcome.

The base-case analyses to be conducted are:

- Cost per hernia clinically detected and cost per additional quality adjusted life (QALY) year gained, both over a two-year period
- Cost per QALY gained at 12 months

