7.4. Randomisation Method

Participants will be randomised into the ROCSS trial in a 1:1 ratio of mesh reinforcement to control (standard closure without mesh). A 'minimisation' procedure using a computer-based algorithm will be used to avoid chance imbalances in important prognostic variables.

The minimisation variables will be:

- 1. Stoma type ileostomy versus colostomy.
- If stoma involves an ileostomy and colostomy, it will be stratified into the colostomy group as the current literature shows that colostomies are at a higher risk of hernia than ileostomy¹¹.
- 2. Surgical incision reopening of midline wound or stoma site only.
- 3. Skin closure type primary or secondary.

8. Treatment and Follow-Up

Please see Appendix B for a detailed patient pathway for the day of surgery.

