Two main analyses will be carried out to evaluate the relative cost-effectiveness of biological mesh reinforcement compared to standard closure. A cost-effectiveness analysis will be based on the cost per improvement from the HerQLes tool. In addition, a cost-utility analysis will be carried out and presented in terms of the cost per additional quality adjusted life-year (QALY) gained. QALYs are multidimensional in that they incorporate both the participants' survival and quality of life. The EQ-5D-5L will be administered as part of the telephone follow-up to derive the additional QALY in the two trial arms. The EQ-5D-5L data will be converted using the EQ-5D-3L crosswalk algorithm and UK tariff values will be applied to generate QALYs. As per the original analysis, QALYs will be calculated using the under-the-area curve method. Costs and QALYs will be discounted at an annual rate of 3.5% as per NICE guidelines.

As participants entered the original trial at different time points and the data collection for the extended follow-up study will take place at a fixed time point, the cost and QALY information will be censored. The analysis will use methods such as inverse probability weighting to take into account the censored nature of the data for the cost-utility analysis.

The total costs and consequences of the interventions will be compared using an Incremental Costeffectiveness Ratio (ICER). For the cost-utility analysis, a threshold of £30,000 per additional QALY gained will be used to assess cost-effectiveness. For the cost-effectiveness analysis, there is no benchmark on the decision maker's willingness to pay for an improvement in the HerQles tool.

The results of these economic analyses will be presented using cost-effectiveness acceptability frontiers to reflect decision uncertainty across different thresholds of willingness-to-pay per additional unit of outcome. Deterministic and probabilistic sensitivity analyses will be undertaken to explore the robustness of the findings to plausible variations in key assumptions and analytical methods used. A

scenario analysis will explore one-off quality of life decrements from the retrospective adverse events from managing hernias (e.g. hospital readmission, reoperation). These retrospective adverse events are likely to impact on participant's quality of life but the gap in data collection has meant that this impact may not be captured.

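### Section 19.12 compares area-under-the-curve QALYs between arms without stating any adjustment for baseline EQ-5D; adding it would be a free improvement.

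*Protocol*

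**What the plan says.** Protocol section 15.1.3 sets out the original trial-based evaluation. Arm-level summaries come first: "For each trial arm, mean costs and outcomes and their 95% confidence intervals will be presented". The estimator follows: "Incremental cost effectiveness ratios (ICERs) will be estimated by dividing the difference in mean cost between two treatments by the difference in mean outcomes". Uncertainty is then handled by bootstrap: "5000 paired estimates of mean differential costs and outcomes will be estimated". No covariate is named, and the sensitivity analyses listed in 15.1.4 do not add one. Complete cases are the base case there.

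Section 15.1.2 provides the utility data: "EQ-5D data will be collected from each patient at baseline (pre-operation), at 30 days postoperation and at 12 and 24 months post-randomisation". Section 7.4 minimises on "Stoma type ileostomy versus colostomy", "Surgical incision reopening of midline wound or stoma site only" and skin closure type, so baseline EQ-5D is not balanced by design.

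Section 19.12 extends the original evaluation to the 5-8 year follow-up. On the QALY itself it says: "As per the original analysis, QALYs will be calculated using the under-the-area curve method". Total costs and consequences are compared through an ICER, with £30,000 per QALY as the decision threshold and acceptability frontiers across other thresholds. Inverse probability weighting is offered for censoring caused by staggered entry. Baseline utility is not mentioned. By contrast, section 19.11 specifies adjusted differences for the primary and secondary clinical outcomes, with covariates not named.

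**The concern.** A patient's QALY total is built from a curve that starts at the baseline score and runs through later scores that are likely to correlate with it. If one arm started with slightly better EQ-5D, its mean QALYs will tend to be higher for reasons unrelated to mesh. A comparison of arm means keeps that difference; a regression on baseline removes its expected effect. The area-under-the-curve rule makes no such correction, and neither do weights for censoring.

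Cost-effectiveness is one of the two aims of ROCSS-EX (section 19.2). The protocol reports no significant quality-of-life difference at two years, so the QALY difference may be small. An imbalance accumulated over 5-8 years could then be comparable with the effect being estimated. Selective loss to follow-up could add imbalance beyond chance: section 19.11 expects data from 588 of the 790 randomised.

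**Working it through.** **Arm sizes (section 19.11).** 790 − 98 = 692 approachable (345 and 347). With 15% dropout, 345 × 0.85 = 293, 347 × 0.85 = 295, total 588. The protocol's figures reproduce. It gives no EQ-5D SD, correlation or QALY difference, so the rest uses stated assumptions.

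**Direct weight of baseline.** By the trapezoid rule with visits at 0, 30 days, 1 year and 2 years, the weights in years are 0.041, 0.500, 0.959 and 0.500 (sum 2.0). Baseline enters the two-year area directly with 0.041/2, about 2%. Any sizeable effect must come through correlation with later scores.

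**Effect of an imbalance D.** Shift in the unadjusted QALY difference = D × [w0 + b × (T − w0)], where w0 is the baseline weight, T the follow-up time and b the slope of later utility on baseline (equal to the correlation r if the SDs are equal). At two years with D = 0.02, the shift is 0.0008, 0.013, 0.020 or 0.028 QALYs for b = 0, 0.3, 0.5 or 0.7.

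**ROCSS-EX.** Assumptions: baseline SD 0.20-0.25, r 0.2-0.5 held constant, mean follow-up about 6.4 years.
- SE of the baseline difference = SD × √(1/293 + 1/295) = SD × 0.0825, giving 0.0165 (SD 0.20) and 0.0206 (SD 0.25).
- Shift for a 1-SE imbalance ≈ r × SE × 6.4 (the small direct term is ignored). Low: 0.2 × 0.0165 × 6.4 = 0.021. High: 0.5 × 0.0206 × 6.4 = 0.066 QALYs.
- At £30,000 per QALY: about £630 to £1,980 per participant, undiscounted.
- Discounting at 3.5%: average factor (1 − 1.035^−6.4)/(6.4 × ln 1.035) = 0.198/0.220 = 0.90, giving about £570 to £1,780.
- Fading correlation: over 6.4 years the final score has trapezoid weight (6.4 − 2)/2 = 2.2. If its correlation with baseline were zero and the others were unchanged, the shift would fall by 2.2/6.4, about 34%. If all correlations were zero, only the direct term would remain: 0.041 × 0.0206, under 0.001 QALY.

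**Simulation of the two estimators.** 4,000 trials, 335 per arm, two-year QALYs, SD 0.25, one common correlation between all visits, no true effect:

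| r | slope of unadjusted difference on imbalance | slope of adjusted difference | SD unadjusted | SD adjusted | variance cut |
|---|---|---|---|---|---|
| 0 | 0.04 | 0.00 | 0.0230 | 0.0230 | none |
| 0.3 | 0.65 | 0.03 | 0.0285 | 0.0256 | 19% |
| 0.5 | 1.01 | −0.01 | 0.0318 | 0.0251 | 38% |
| 0.7 | 1.41 | 0.00 | 0.0346 | 0.0220 | 60% |

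The variance cut is 1 − (SD adjusted/SD unadjusted)². The mean unadjusted difference was within 0.001 of zero throughout, so the estimator is unbiased. What adjustment removes is its dependence on the imbalance and part of its variance.

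**The case against.** The strongest reply is that the protocol never says the difference is unadjusted. A difference in mean cost over a difference in mean outcomes is the usual definition of an ICER, and adjusted means would satisfy it. Covariates are commonly left to an analysis plan, and section 19.11 already promises adjusted differences for continuous secondary outcomes, of which EQ-5D is one. This stands in part: the wording does not exclude adjustment. But QALYs are not named in 19.11, the pointer to a separate analysis plan sits there rather than in section 15 or 19.12, and the one economic estimator that is written down has no covariate.

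Several stronger readings are tempting and are not supported.
- A reader might infer that the QALY difference is biased. It is not, over repeated randomisation; chance imbalance is sampling error that an interval or acceptability curve already reflects. The loss is error conditional on the imbalance that occurred, and precision.
- A reader might infer that ROCSS-EX will bootstrap unadjusted means. The reference in 19.12 to the original analysis attaches only to how QALYs are calculated, and 19.12 mentions no bootstrap.
- A reader might infer that the baseline score distorts the result because it is part of the area. Its direct share is about 2% at two years.
- A reader might infer that imbalance will decide the verdict at £30,000. The protocol gives no incremental cost, so this cannot be shown, and results are also to be presented across thresholds.

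**Conclusion.** The point holds as a recommended improvement. Section 19.12 extends an evaluation whose only stated estimator is a difference in arm means, and does not say that the QALY comparison will use the baseline EQ-5D the trial already holds. Under the assumptions shown, a one-standard-error imbalance is worth about 0.02-0.07 QALYs, or £630-£1,980 per participant undiscounted and roughly 10% less discounted. These figures depend on an SD and a correlation that the protocol does not give, and on that correlation persisting from a score taken with the stoma in place to one 5-8 years later. They shrink if it fades and vanish in practice if it is zero. The two-year analysis under 15.1.3 has already been reported; nothing here shows that its result is wrong.

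**What to change.** In section 19.12, state that incremental QALYs will be estimated by regression on arm with baseline EQ-5D utility as a covariate, combined with the planned weights for censoring. The three minimisation factors may be added but are optional. Use the adjusted difference in the ICER, in the acceptability frontier and in whatever resampling is used for uncertainty, refitting the model in each resample. Report the unadjusted difference as a sensitivity analysis. Section 15.1.3 needs aligning only if the two-year analysis is re-run. The cost is a sentence or two of text and one covariate already in the database, with no new data collection.
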